14.1 Demographic and Baseline Characteristics

The following demographic variables at screening will be summarized by dose level: sex, age, and weight.

14.2 Analysis of Primary Endpoint

We will use generalized estimating equations (GEE) to compare mean change from baseline to 2-hour time-points in high-dose vs. low-dose, controlling for repeated measures.

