STATISTICS Primary Analysis Plan	To detect a mean difference of 3 cm (SD 3) on the change in VAS between doses, an effect size that has been considered clinically meaningful in previous pediatric migraine work, we would anticipate needing 2-hour outcome data on 16 individuals per arm for subjects treating only one attack. However, we will be able to control within subject variability to a degree by having subjects treat two attacks, and thus will revise the estimate to needing outcome data on 12 per group. We will use generalized estimating equations (GEE) to compare mean change from baseline to 2-hour time-points in high-dose vs. low-dose, controlling for repeated measures.
Rationale for Number of Subjects	
Assuming 15% drop-out, and adding an extra 20% data-loss for those who will be asleep at the 2-hour time point assessment, we anticipate needing to enroll 19 participants per dosing arm. As we wish to be able to perform this analysis both for the group overall (i.e. all “high dose” vs. all “low dose”), and for the <40 kg and ≥40 kg subgroups individually, we will need to enroll a total of 76 participants.
 
19 @ < 40 kg, given 1 mg at each of 2 attacks 19 @ < 40 kg given 4 mg at each of 2 attacks 19 @ ≥40 kg given 2 mg at each of 2 attacks 19 @ ≥40 kg given 8 mg at each of 2 attacks

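### GEE is planned with no small-sample correction: under the usual default, a nominal 5% test would run at about 5.7–6.1% overall and 6.4–7.4% within weight strata

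*Combined protocol and SAP*

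**What the plan says.** Section 14.2 gives the primary analysis as: "We will use generalized estimating equations (GEE) to compare mean change from baseline to 2-hour time-points in high-dose vs. low-dose, controlling for repeated measures". The synopsis repeats this under Primary Analysis Plan. Neither place states a working correlation, a standard error, a correction for few participants, degrees of freedom or a significance level. The opening of section 14 promises a SAP before the final analysis, but no further detail on this analysis appears.

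The synopsis sets the size. The target is "To detect a mean difference of 3 cm (SD 3) on the change in VAS between doses", for which "we would anticipate needing 2-hour outcome data on 16 individuals per arm for subjects treating only one attack". Because each participant treats two attacks, the investigators "will revise the estimate to needing outcome data on 12 per group". Allowance is then made for losses ("Assuming 15% drop-out, and adding an extra 20% data-loss for those who will be asleep at the 2-hour time point assessment"), giving "we anticipate needing to enroll 19 participants per dosing arm". The comparison is wanted for both doses overall "and for the <40 kg and ≥40 kg subgroups individually, we will need to enroll a total of 76 participants". The overall comparison is the primary objective (section 3.1); the weight-stratum comparisons are secondary (section 3.2).

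**The concern.** Dose is assigned to participants, so the number of participants, not of attacks, determines how well the robust standard error behaves. At the planned minimum there are 2 × 12 = 24 participants with data per weight stratum and 4 × 12 = 48 overall, each contributing at most two attacks. The standard robust (sandwich) variance and the normal reference distribution are both large-sample approximations. With few participants both err in the same direction: the standard error is too small and the critical value is too low.

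At stake is how much certainty is attached to the estimated difference between doses, overall and in each weight band. The strata were sized for their own comparisons, and each compares a different pair of doses.

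**Working it through.** **The plan's own figures.** With difference 3 and SD 3, n per arm = 2 × (1.960 + 0.842)² × (3/3)² = 15.7, so 16. This assumes 5% two-sided and 80% power, neither of which is stated; one-sided 5% would give 13, and 90% power two-sided would give 22. Averaging two attacks with within-person correlation ρ multiplies the requirement by (1 + ρ)/2, and 16 × (1 + ρ)/2 = 12 gives ρ = 0.5. Enrolment is 12/(1 − 0.35) = 18.5, so 19 per arm and 4 × 19 = 76. All the stated numbers reproduce.

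**True size of the default test.** With two attacks per participant and n participants per dose group, the GEE estimate is the difference between the two groups' averages of participant means. The uncorrected sandwich variance divides by n where n − 1 is needed, so the standard error is too small by the factor √((n − 1)/n). Referring the result to 1.96 gives, for normal outcomes,

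size = P(|t on 2n − 2 df| > 1.96 × √((n − 1)/n)).

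| Comparison | Evaluable per dose group, n | SE factor | Effective cut-off | df | True size |
|---|---|---|---|---|---|
| Stratum, planned minimum | 12 | 0.957 | 1.877 | 22 | 7.4% |
| Stratum, 15% drop-out only (0.85 × 19 ≈ 16) | 16 | 0.968 | 1.898 | 30 | 6.7% |
| Stratum, no loss | 19 | 0.973 | 1.908 | 36 | 6.4% |
| Overall, planned minimum | 24 | 0.979 | 1.919 | 46 | 6.1% |
| Overall, 15% drop-out only | 32 | 0.984 | 1.929 | 62 | 5.8% |
| Overall, no loss | 38 | 0.987 | 1.934 | 74 | 5.7% |

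**Check by simulation** (null effect, 100,000 data sets per setting):

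- 12 per arm: 7.3–7.5% for ρ from 0.2 to 0.8, and 7.6% if 20% of attacks are also missing.
- 24 per dose: 6.1%, or 6.5% if weight stratum enters as a covariate.
- A standard GEE routine at its default settings (3,000 data sets): 7.1% at 12 per arm and 6.3% at 24 per dose.

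**After correction.** A Kauermann-Carroll standard error with a t reference on participants minus parameters gave 4.9–5.1% at 12 per arm and 5.0% overall. In the balanced, complete case it reduces to the ordinary two-sample t test on participant means.

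**Cost in width.** Per stratum at 12 per arm: √(12/11) × 2.074/1.960 = 1.105. Overall at 24 per dose: √(24/23) × 2.013/1.960 = 1.05.

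**Cost in power at 12 per arm.** With ρ = 0.5 the SD of a participant's mean is 3 × √0.75 = 2.598, and the standardised difference is 3/(2.598 × √(2/12)) = 2.83. The normal approximation gives Φ(2.83 − 1.96) ≈ 80.7%; the non-central t on 22 df gives 77.1%.

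**The case against.** The strongest reply is that the plan never prescribes the faulty test. It says GEE, and GEE can be run with model-based or corrected variances and a t reference; a SAP is still to come. That stands: a reader might infer that the plan commits to an uncorrected sandwich with a normal reference, and the documents do not say so. The finding is conditional on the usual default. A model-based standard error would not by itself remove the problem: with a normal reference it gave 6.4% at 12 per arm and 6.1% at 24 per dose in the same 3,000-data-set check.

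Twelve per arm is also a minimum target, not the expected sample. Sleep removes a 2-hour reading for one attack, so a child asleep in one attack may still contribute the other. The awake-completer analysis is listed as a sensitivity analysis, which suggests that sleepers need not be dropped from the main one. The synopsis also lists 100 subjects against the 76 in the sample-size text; 25 per arm with 35% loss again leaves about 16. This stands too, and is why a range is given. The inflation shrinks with more data but remains.

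A reader might go further and infer that a dose could be carried forward on a difference that fails the trial's stated significance level. The documents do not support that. No level is stated, and the selection rule in section 2 and the synopsis (most effective, then best tolerated, then lowest effective dose) names no significance threshold.

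**Conclusion.** The point holds as a modest one. Under the usual default, the primary overall comparison runs roughly 0.7 to 1.1 percentage points above a nominal 5%, with a standard error 1–2% too small. The secondary stratum comparisons run about 1.4 to 2.4 points above, with a standard error 3–4% too small. It would be wrong to attach the 7% figure to the primary analysis.

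The figures rest on four assumptions: an uncorrected robust standard error with a normal reference; a two-sided 5% level, inferred from the 16 per arm; approximately normal changes in VAS with equal spread in the two groups; and between 12 and 19 evaluable participants per arm. They depend little on the within-person correlation. In an open-label pilot that feeds a later placebo-controlled trial, the practical effect is small. It is still worth removing, because a better-calibrated method is available for one sentence of text.

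**What to change.** In section 14.2, the synopsis and the SAP, keep GEE and add that every VAS comparison, overall and by weight stratum, uses a small-sample corrected robust variance (for example Kauermann-Carroll) with a t reference on number of participants minus number of parameters. A random-intercept mixed model with Kenward-Roger degrees of freedom is an acceptable alternative. State the confidence level in the same sentence.

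The cost at the planned minimum is intervals about 10% wider per stratum and 5% wider overall, and less with more evaluable participants. The power implied for a stratum comparison at 12 per arm drops from about 81% to about 77%; holding 80% there would take 13 evaluable per arm. No extra patients are proposed, but the lower figure should be acknowledged in the sample-size text.

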doses being studied here are well within the range of what has been safely studied in children before. We propose, depending on weight, to give between 1 mg and 8 mg of melatonin, once, at onset of headache. Each participant would treat two attacks. As noted above, neonates have safely been given 10mg/kg IV for peri-procedural pain management. Children undergoing auditory brainstem response tests were given 5-20 mg. Doses of 0.25-0.5 mg/kg have been given for MRI sedation—which would equate to about 15 mg for a 30 kg child. In another study, children were given 10 mg for MRI sedation. Our clinical experience suggests that for acute migraine treatment, 1-4 mg of melatonin would be adequate for children < 40 kg, and 2-8 mg for children and adolescents >40 kg. We propose to study a melatonin formulation that is an edible (i.e. chewable) milk-chocolate based formulation. We consider this formulation to have three potential advantages:

1. More rapid onset than a tablet/capsule formulation, potentially allowing for faster relief and in turn potentially a higher chance of relief, as treating when the pain is still mild has been shown to predict efficacy of other acute migraine treatments.
2. Young children who cannot yet swallow pills will be able to take this formulation.
3. Children who are nauseated during migraine attacks may still find a chocolate-based formulation palatable and be willing to take it during an attack.

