3.2 Secondary Objectives

- To determine a change in mean VAS score between baseline and 2-hr time point in low-dose vs. high-dose group in the < 40 kg and the ≥ 40 kg subgroups. (We will also do sensitivity analyses of completers who were awake for the 2-hr time point).

- To determine the tolerability/side effects of high-dose vs. low-dose in the group over all, and in weight-based strata.
- To determine the proportion of participants who get to mild/no pain by 2 hrs (overall and by weight group), and who remain at mild/no pain from 2-24hours
- To determine the proportion of participants who get to mild/no of each of: pain, photophobia, phonophobia, nausea, vomiting at 30, 60, 90, and 120 minutes and 24 hours; both overall and in weight based strata.
- To determine the proportion of parents/participants who found the treatment useful, and who preferred it over other treatments they'd tried.
- Using logistic regression, we will examine for possible predictors of treatment efficacy (sex, age, nap, nap duration, etc).
- To determine the proportion of participants who needed rescue medication between 2-24 hrs, both overall and by weight- based strata.

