4 STUDY DESIGN

4.1 Study Overview

This randomized pilot trial is a dose finding study to determine which dose of melatonin is most effective for treating acute migraine in children and adolescents who have episodic migraine. Participants will be randomized to a higher-dose or a lower-dose, stratified by weight (< 40 kg and \geq 40 kg). They will treat 2 acute headache attacks and will complete a symptom diary for those 2 attacks and then return the diary to the study center. Randomization will be done in blocks of 4 to ensure equal group size and will be stratified by weight (< 40 kg or \geq 40 kg).

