8.2 Blinding

This is an open label study and there is no blinding

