Chocolate melatonin supplies will be given to the parents for all young children who, in the opinion of the investigator, may need additional supervision. If a child were to eat all of the chocolate melatonin pieces at once, this would still be considered a safe amount, as neonates have been safely given 10mg/kg IV melatonin³.

They will also be given a paper headache diary (either in person or shipped). They will be instructed to treat as early as possible in an attack, i.e. ideally while the pain is still mild, however they will still be permitted to treat even if the pain has reached the moderate or severe levels. Participants will be asked to treat attacks that occur at home (or attacks that are not yet treated when they reach home), or that occur at another location where they can stay for at least 8 hours if needed, so as to ensure driving after dosing will not be necessary (for older teens), and that headache diaries will be available, and participants can sleep after dosing if desired.

Participants will record baseline pain intensity (and other migraine symptom intensity) at time zero, i.e. right before they dose the melatonin. They will be asked not to take other acute medications for two hours, and to record pain intensity (and other symptom intensity) at 30, 60, 90 min and the two-hour time marks. If they fall asleep, parents/caretakers will be instructed **not** to wake them for data collection, as sleep may be a mechanism by which melatonin helps acute

migraine. They will resume data collection as soon as they first awaken. They will be asked to collect data also at 4 hours and 24 hrs, and to record any acute medication used between 2-24 hours. They will also be asked to record their impressions about the treatment's efficacy, side effects, and whether or not they slept after dosing and if so for how long.

Study staff will contact participants until they complete the study to remind them about when to treat an acute attack and to answer any questions. Participants may be sent 'retention' packages (small office supplies, pens, or other small items) to remind them about the study. At the completion of the study, participants will be asked to mail back the headache diary in a pre-paid FedEx envelope. A \$5 gift card will be given to participants once they mail back the diary.

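### The primary GEE names no term for time-zero VAS or the weight stratum; the test is not invalidated and keeps its planned power, but it may forgo precision

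*Combined protocol and SAP*

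**What the plan says.** The primary model is stated in the Protocol Synopsis (Statistics) and in section 14.2, in the same terms: "generalized estimating equations (GEE) to compare mean change from baseline to 2-hour time-points in high-dose vs. low-dose, controlling for repeated measures". Dose and repeated measures are the only elements named.

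Two candidate terms are already available:

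- **Time-zero VAS.** Section 10.1: "Participants will record baseline pain intensity (and other migraine symptom intensity) at time zero", at each treated attack. Early treatment is encouraged, but "they will still be permitted to treat even if the pain has reached the moderate or severe levels", so pain at dosing can vary between attacks. Section 1.2 remarks that "treating when the pain is still mild has been shown to predict efficacy of other acute migraine treatments".
- **Weight stratum.** Section 4.1: "Randomization will be done in blocks of 4 to ensure equal group size and will be stratified by weight". Section 8.1 repeats this.

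The exploratory logistic regression in section 3.2 does not list pain at dosing ("we will examine for possible predictors of treatment efficacy (sex, age, nap, nap duration, etc"), although the open-ended list leaves room for it. The baseline summary in section 14.1 covers sex, age and weight only. Section 14 defers fuller detail to a SAP that is still to be written.

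**The concern.** A baseline value of the outcome and the stratification factor are the two covariates a reader would expect in this model. Both are collected and neither is named. If time-zero pain predicts 2-hour pain in a way that the change score does not fully absorb, the interval for the dose difference is wider than it need be.

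That matters most for the secondary comparisons within each weight group, planned on 12 evaluable participants per arm. For the pooled comparison, the stake is a tighter interval when choosing the dose to carry forward. Leaving the terms open until data are in hand also leaves a later choice between adjusted and unadjusted results.

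**Working it through.** **1. The plan's own figures.** The Synopsis gives a difference of 3 cm and an SD of 3 cm on the change in VAS. Alpha and power are not stated; two-sided 0.05 and 80% are inferred because they return the plan's number.

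- One attack: 2 × (1.96 + 0.84)² × 3²/3² = 15.7, so 16 per arm, as stated.
- Two attacks: the plan says "thus will revise the estimate to needing outcome data on 12 per group". This equals 16 × (1 + 0.5)/2 = 12, so it implies a correlation of 0.5 between attacks.
- Loss of 15% + 20%: 12/(1 − 0.35) = 18.5, so 19 enrolled, as stated.

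**2. Power of the analysis as planned.** The variance of a participant's mean change over two attacks is 9 × 0.75 = 6.75. At 12 per arm the standard error is √(2 × 6.75/12) = 1.06 cm, and power for 3 cm is 0.771 by t (0.807 by normal approximation). Pooled, at 24 per arm, the standard error is √(2 × 6.75/24) = 0.75 cm and power is 0.975 by t. The input SD is the SD of change, so omitting covariates takes nothing from these figures.

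**3. What adjusting for time-zero VAS could add.** With r the baseline-to-2-hour correlation and k = baseline SD/2-hour SD, neither of which the documents give:

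unadjusted/adjusted CI width = √[(1 + k² − 2rk)/(1 − r²)]

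This assumes that r, and so the baseline slope r/k, is the same between and within participants. Example, k = 1.0 and r = 0.3: √(1.40/0.91) = 1.240. The pooled half-width is 2.01 × 0.75 = 1.51 cm unadjusted; the last column divides this by the ratio.

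| k | Extra unadjusted width at r = 0.3 / 0.5 / 0.7 | Adjusted pooled half-width, cm |
|---|---|---|
| 0.5 | 2.2 / 0.0 / 3.8% | 1.45–1.51 |
| 0.7 | 8.4 / 2.6 / 0.0% | 1.39–1.51 |
| 1.0 | 24.0 / 15.5 / 8.5% | 1.22–1.39 |
| 1.2 | 37.5 / 28.6 / 22.1% | 1.10–1.24 |

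The gain is zero where r = k. With the SD of change held at 3, a baseline SD of 1.5 or 2.0 cm gives 0–9%.

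Plausibility: the 2-hour SD implied by an SD of change of 3 is 3/√(1 + k² − 2rk). At k = 1.0 this is 2.5 to 3.9 cm. A uniform spread on an assumed 10 cm scale has SD 10/√12 = 2.9 cm, and some settings at every k need more than that at one of the two time points.

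**4. Simulation at 12 per arm.** Two attacks per participant, attack correlation 0.5, exchangeable GEE, equal slopes, and the same small-sample (Kauermann-Carroll) t-test for both analyses; 20,000 trials per setting. Unadjusted power was 0.766–0.776. Adjusting changed it by −1 to +5 points at k = 0.5–0.7, +5 to +14 at k = 1.0 and +13 to +19 at k = 1.2.

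**5. Unequal slopes.** Time-zero VAS varies within participants, so the equal-slope condition may fail. With an assumed between-participant slope of 1 and within-participant slope of 0–0.3, the adjusted standard error was about 2–3% larger at 12 per arm, about 2% larger at 24 and 0.9–1.5% larger at 200. A second simulation of unequal slopes gave 0.7% smaller to 0.8% larger.

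**6. Stratum term.** A gap g in mean change between equal-sized weight groups adds g²/4 to the variance when the stratum is omitted:

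- g = 1 cm (assumed): √(7.00/6.75) − 1 = 1.8% extra pooled width.
- g = 2 cm (assumed): √(7.75/6.75) − 1 = 7.2%.

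The unadjusted test is then conservative: simulated size 4.2–4.8% and 3.5–3.9% against a nominal 5%.

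**The case against.** The strongest reply is that nothing is broken. Design and analysis match, both being based on change; covariates normally belong in the SAP; and the possible gain runs from nothing to 37% on values that the documents do not give. At k = 0.5–0.7 the pooled half-width moves by at most 0.12 cm against a 3 cm target, with power already near 97%. All of this stands, and it is why the point is an improvement and not an error.

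A reader might infer that adjustment can never lose precision, or that the most it can cost is about 1 point of power. Both hold only with equal slopes (the first in large samples), and the documents offer nothing to establish that. The unequal-slope results show small losses.

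The second serious objection concerns the covariate itself. Section 8.2 says "This is an open label study and there is no blinding", and section 10.1 has participants told their dose, so time-zero VAS is recorded after known allocation; for attack 2 it also follows treatment of attack 1. A dose-related difference in time-zero VAS would separate the two estimates by (1 − r/k) cm per 1 cm of difference, from −0.4 (r = 0.7, k = 0.5) to +0.75 (r = 0.3, k = 1.2), and the data could not show which is right. This stands as a reason to report both analyses. It does not favour the planned one, because the change score uses the same time-zero value. The stratum term does not carry this problem.

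The remark in section 1.2 is also weak support: it concerns other treatments and gives no correlation. It makes time-zero pain a sensible candidate and does not size the gain.

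**Conclusion.** The point holds as a cheap improvement. Neither covariate is named, and the planned comparison may be less precise than it could be. The possible size is 0–8% of CI width at k = 0.5–0.7, 8–24% at k = 1.0 and 22–37% at k = 1.2, assuming r = 0.3–0.7 and equal slopes. It could be nil, or a loss of up to a few percent of the standard error, if the slopes differ. The stratum adds 1.8–7.2% under assumed gaps of 1–2 cm. The benefit of fixing the model before data are seen depends on none of these assumptions.

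A reader might also infer that the trial is underpowered or its primary test invalid because of the omission. The documents do not support that: the SD is stated for the change, and leaving out the stratification factor makes the test conservative. Validity here refers to the omitted terms only. An uncorrected sandwich z-test is mildly liberal at 12 per arm with or without them (simulated at about 9% and 7–8% respectively), which is a separate matter.

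**What to change.** In section 14.2 and the SAP, specify the primary GEE with dose arm, weight stratum and time-zero VAS for that attack, and name the working correlation, since it affects how between- and within-participant slopes are mixed. Within each weight group, use the same model without the stratum term. Report the unadjusted change analysis alongside, and summarise time-zero VAS by arm and attack so that any dose-related baseline difference is visible.

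The cost is a sentence or two and one extra table; all the data are already collected. The statistical cost is about 1 point of power at 12 per arm in the least favourable equal-slope settings, or up to a few percent of the standard error if the slopes differ.
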